3.4 Slide Allocation

For each participant, the 102 WSIs are randomly divided into three disjoint subsets (SX, SY1, SY2), each containing 34 slides. The allocation is stratified by APL status to ensure balanced representation of positive and negative cases across all three conditions.

Key principles:

- No slide is shown to the same reader more than once.
- Slide allocation is unique to each reader.
- Stratification ensures a comparable APL prevalence across all three subsets for each reader.

- Randomization minimizes bias from case difficulty or other confounders.

3.5 Study Workflow

Each participant completes a study session with the following structure:

1. **Randomization:** Participant is randomly assigned to Arm A or Arm B.
2. **Block sequence setting:** Participant completes blocks in the assigned order (X→Y or Y→X), depending on their Arm assignment.
3. **Slide sequence setting:** Participant review slides according to a predefined randomized order. The sequence is different for each participant.
4. **Pre-study briefing:** Participants receive instructions on the review platform; They also review two mock slides, one unaided, one aided, to familiarize themselves with the testing platform.
5. **Data recording:** For each slide, the system automatically records:
 - Diagnosis (APL vs. non-APL)
 - Confidence score (1-5 scale)
 - Time to decision (in seconds)
 - For Y1 (AI as Double-Check): both pre-AI and post-AI diagnoses and confidence scores

3.6 AI System (LEAP) Implementation

The LEAP AI system generates diagnostic predictions independently for all 102 WSIs before the study session begins. During the study:

- **Condition X (Unaided):** AI predictions are not shown to the clinician
- **Condition Y1 (AI as Double-Check):** AI prediction is revealed only after the clinician submits their initial diagnosis
- **Condition Y2 (AI as First Look):** AI prediction is visible throughout the review

AI predictions are presented as binary classifications (APL vs. non-APL).

3.7 Masking and Blinding

The study employs triple masking:

- **Patients:** Patients are blinded to the study arm to which their samples are assigned.
- **Care Provider:** Clinicians are blinded to the ground-truth diagnoses during all review sessions.
- **Investigator:** Study coordinators administering the session are blinded to the ground-truth diagnoses and to participants' arm assignments. In addition, statistical analysts are blinded to participant identities and arm assignments before results are finalized.

3.8 Ground Truth Determination

The reference standard diagnosis for each case is established using flow cytometry, immunohistochemical staining of trephine needle BM biopsies, cytogenetic analysis, and genomic testing.

4. STUDY POPULATION

4.1 Participating Clinicians (Readers)

4.1.1 Target Enrollment

Planned: 10 participants

Actual: 10 participants

4.1.2 Inclusion Criteria for Readers

- Board-certified pathologists who routinely interpret hematopathology specimens in clinical practice, OR board-certified or board-eligible hematologists who routinely make hematopathology diagnoses in clinical practice.
- Willingness and ability to complete both unaided and AI-assisted review sessions.
- Familiarity with microscopic interpretation of Wright-Giemsa-stained bone marrow aspirate smears.

4.2 Patients

4.2.1 Sample Size

The number of cases reviewed per participating clinician: 102 Wright-Giemsa-stained bone marrow aspirate WSIs from 102 patients

Distribution per condition: 34 slides for Condition X, 34 slides for Condition Y1, 34 slides for Condition Y2

4.2.2 Inclusion Criteria for Cases

- Wright-Giemsa-stained bone marrow aspirate smear digitized as a whole-slide image.
- Adequate specimen quality and cellularity for diagnostic interpretation.
- Final diagnosis confirmed through molecular testing and established ground-truth.

4.2.3 Exclusion Criteria for Cases

- Poor-quality or technically inadequate slides (e.g., inadequate staining, crush artifact).
- Unreadable or corrupted digital images.
- Cases used in the training or internal validation of the LEAP AI model.

5. STUDY PROCEDURES

5.1 Pre-Study Procedures

5.1.1 *AI Prediction Generation*

Prior to participant enrollment, the LEAP AI system generates diagnostic predictions for all 102 study cases. AI predictions are stored securely and revealed to participants only according to the assigned study condition.

5.1.2 *Randomization Procedures*

- Participants are randomized to Arm 1 (X→Y) or Arm 2 (Y→X) using a computer-generated randomization sequence with size 2 and size 4 blocks.
- For each participant, slides are randomly allocated to subsets SX, SY1, and SY2 with stratification by APL status
- All randomization is performed using validated software and documented in the study database.

5.2 Study Session Procedures

5.2.1 *Reader Orientation*

At the beginning of the study session, readers receive:

- Instructions on using the digital slide review platform
- Explanation of the three review conditions (X, Y1, Y2)
- Descriptions of the confidence rating scale (1-5)
- Opportunity to ask questions and practice with example slides not included in the study set

5.2.2 *Slide Review Process*

For each slide, readers:

1. Review the digitized WSI using the study platform with zoom and navigation capabilities
2. Formulate a diagnosis (APL vs. non-APL)
3. Assign a confidence score (1 = Random Guess; 2 = Very Doubtful; 3 = Unsure; 4 = Mostly Certain; 5 = Absolutely Certain)

4. Submit their decision (or initial decision in Condition Y1)
5. **For Condition Y1 only:** After submission, view AI prediction and optionally revise diagnosis and confidence rating
6. Proceed to the next slide

5.2.3 Data Capture

The study platform automatically records for each slide:

- Reader ID (de-identified)
- Slide ID (de-identified)
- Study condition (X, Y1, or Y2)
- Diagnosis (APL vs. non-APL)
- Confidence score (1-5)
- Time from slide presentation to diagnosis submission (in seconds)
- For Condition Y1 only:
 - Pre-AI diagnosis and confidence score
 - Post-AI diagnosis and confidence score
- Timestamp of review

5.2.4 Session Duration

Participants complete all 102 slides in a single session. The expected duration is approximately 2-3 hours, with optional breaks permitted. The study platform allows participants to pause between slides but not during the review of an individual slide.

5.3 Study Completion

Actual Study Start Date: September 9, 2025

Actual Study Completion Date: October 10, 2025

Actual Number of Participants: 10

Actual Number of Slides per Participant: 102 (34/34/34)

Actual Number of Total Diagnostic Decisions in This Study: 1,020

6. OUTCOME MEASURES

6.1 Primary Outcome Measure

6.1.1 Diagnostic Performance of APL Detection

Measurement Time Frame: Periprocedural (at the time of slide review)

Description: The primary outcome is the diagnostic performance of clinicians in detecting APL, evaluated separately for each of the three study conditions (X, Y1, Y2). Performance will be measured using the following metrics:

- **Accuracy:** Proportion of correct diagnoses (both APL and non-APL cases)
 - Formula: $(TP + TN) / (TP + TN + FP + FN)$
- **Sensitivity:** Proportion of true APL cases correctly identified as APL

- Formula: $TP / (TP + FN)$
- **Specificity:** Proportion of true non-APL cases correctly identified as non-APL
 - Formula: $TN / (TN + FP)$
- **Positive Predictive Value (PPV):** Proportion of cases diagnosed as APL that are truly APL
 - Formula: $TP / (TP + FP)$
- **Negative Predictive Value (NPV):** Proportion of cases diagnosed as non-APL that are truly non-APL
 - Formula: $TN / (TN + FN)$

Where: TP = True Positive, TN = True Negative, FP = False Positive, FN = False Negative

6.2 Secondary Outcome Measures

6.2.1 Time to Diagnosis

Measurement Time Frame: Periprocedural (at the time of slide review)

Description: Time in seconds required to reach a diagnostic decision for each case. This will be calculated as the elapsed time from when the slide is displayed to when the participant submits their diagnosis. For Condition Y1, both pre-AI and post-AI (total) review times will be recorded. Time will be compared across the three conditions to assess whether AI assistance affects diagnostic efficiency.

6.2.2 Inter-Observer Variability

Measurement Time Frame: Periprocedural (at the time of slide review)

Description: Agreement among clinicians across the three conditions, measured using inter-rater reliability metrics:

- Cohen's kappa (for pairwise agreement)

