7.3.2 Inter-Observer Variability

Statistical Method:

- Cohen's kappa will be calculated to assess overall inter-rater agreement.

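### Kappa alone cannot show whether readers agree more on the correct diagnosis or only on the LEAP call they all saw

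*Combined protocol and SAP*

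**What the plan says.** Inter-observer variability is a secondary outcome in its own right. Section 6.2.2 describes it as "Agreement among clinicians across the three conditions, measured using inter-rater reliability metrics" and lists only Cohen's kappa, for pairs of readers. The analysis text in 7.3.2 is one line: "Cohen's kappa will be calculated to assess overall inter-rater agreement". Neither section gives a contrast between conditions, a test, an interval or a rule for interpretation. Neither says whether the pre-AI or the post-AI diagnosis represents Y1, although 3.5 and 5.2.3 record both.

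On the AI cue, 3.6 states: "The LEAP AI system generates diagnostic predictions independently for all 102 WSIs before the study session begins". The call is shown as APL or non-APL, the same scale as the reader's own diagnosis. In Y1, "AI prediction is revealed only after the clinician submits their initial diagnosis"; in Y2, "AI prediction is visible throughout the review".

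**The concern.** Two readers who meet the same slide with AI see the same call. To the extent that they follow it, they agree with each other, whether or not it is right. Kappa gives the same credit to two readers who share a wrong diagnosis as to two who share the right one. If every reader copied LEAP and LEAP used both labels, kappa would be 1 whatever LEAP's accuracy. In X there is no such cue, so comparing X with Y2 or post-AI Y1 mixes better reading with shared following.

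This matters because section 1.3 gives inter-observer variability in microscopy as part of the reason for the study. A higher kappa under AI would invite a statement that LEAP makes diagnosis more consistent, when part of the rise may be shared error.

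**Working it through.** **The plan's own figures.** 10 readers × 102 slides = 1,020 decisions, as in 5.3. No kappa, power or sample-size figure is stated. Ten readers form 10 × 9 / 2 = 45 pairs. Slides are split at random into thirds separately for each reader (3.4), so two readers have a given slide in the same named condition with probability 1/3 × 1/3 = 1/9. A pair therefore shares on average 102/9 = 11.3 slides per condition, and the 45 pairs together have 45 × 102/9 = 510 pair-reads per condition.

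**An identity that needs no model.** On shared reads let BC, BW and D be the shares both correct, both wrong and split. BC + BW + D = 1 and mean accuracy A = BC + D/2, so BC − BW = 2A − 1. If accuracy on these reads is flat, any rise in raw agreement (BC + BW) is therefore half both-correct and half both-wrong.

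**A simple model for size.** All inputs are assumptions. Reader accuracy is a = 0.85, LEAP accuracy L (sensitivity equal to specificity for both), and APL prevalence π = 1/3. With AI, each reader takes LEAP's call with probability w and otherwise gives their own. Unaided errors of two readers correlate at ρ; LEAP's errors are independent of the readers'. With e = 1 − a and l = 1 − L:

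- A = wL + (1 − w)a
- BW = w²l + 2w(1 − w)le + (1 − w)²[e² + ρe(1 − e)]
- BC = 2A − 1 + BW
- p = πA + (1 − π)(1 − A), and chance agreement Pe = p² + (1 − p)²
- kappa = (BC + BW − Pe) / (1 − Pe)

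Worked case, L = 0.85, w = 0.5, ρ = 0:

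- A = 0.85 throughout, p = 0.3833, Pe = 0.5272.
- Unaided: BW = 0.15² = 0.0225, BC = 0.7225, kappa = (0.745 − 0.5272)/0.4728 = 0.46.
- Aided: BW = 0.0375 + 0.01125 + 0.005625 = 0.0544, BC = 0.7544, kappa = (0.8088 − 0.5272)/0.4728 = 0.60.

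The same formulas give (unaided → aided):

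| L | w | ρ | Accuracy | Kappa | Both correct | Both wrong |
|---|---|---|---|---|---|---|
| 0.85 | 0.5 | 0 | 85% → 85% | 0.46 → 0.60 | 72.3% → 75.4% | 2.3% → 5.4% |
| 0.75 | 0.8 | 0.3 | 85% → 77% | 0.62 → 0.77 | 76.1% → 71.4% | 6.1% → 17.4% |
| 0.75 | 0.5 | 0.3 | 85% → 80% | 0.62 → 0.57 | 76.1% → 69.6% | 6.1% → 9.6% |
| 0.85 | 0.5 | 0.6 | 85% → 85% | 0.78 → 0.68 | 79.9% → 77.4% | 9.9% → 7.4% |
| 0.95 | 0.8 | 0 | 85% → 93% | 0.46 → 0.85 | 72.3% → 89.5% | 2.3% → 3.5% |

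In row 2 kappa rises while both-correct falls. In row 3 kappa falls while both-wrong rises. So kappa's direction does not reveal what happened to either share. A grid over π = 0.20, 0.33 and 0.50 and a = 0.85 and 0.90 gave the same pattern.

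**Simulation of the actual layout** (400 trials per scenario, 34 APL of 102 assumed, L = a = 0.85, w = 0.5, kappa averaged over 45 pairs). Mean kappa went 0.46 → 0.58 at ρ = 0 (rising in 90% of trials), 0.62 → 0.62 at ρ = 0.3 (54%) and 0.77 → 0.66 at ρ = 0.6 (10%). The SD of single-pair kappas was about 0.21 to 0.26, so individual pairs say little.

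**The case against.** The strongest reply is that kappa measures reproducibility, not validity, and that validity is covered elsewhere. Accuracy, sensitivity and specificity by condition are the primary outcome (6.1.1, 7.2.1), so a loss of accuracy would be in the main results. Reader–LEAP concordance is reported by condition (6.2.3, 7.3.3), and harmful changes are counted in Y1 (6.2.4, 7.3.4). A higher kappa is, literally, lower variability between readers.

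Much of this stands, but it leaves a gap. Accuracy is a marginal rate and does not show whether errors are shared. Concordance is not split by whether LEAP was right. Harmful changes can be counted only in Y1, so Y2, where the cue is present throughout, has no counterpart. Both-wrong shares could be derived from raw agreement and accuracy on shared slides, but the plan commits to reporting neither.

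Three stronger readings are tempting and are not supported:

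- **That the shared cue makes kappa rise.** It can, but if readers already tend to err on the same slides, moderate following can leave kappa flat or lower it. Common hard smears make some correlation plausible.
- **That the plan would count a higher kappa as a benefit.** A reader might infer this from the outcome's name and the rationale. No section sets a kappa test, direction or benefit rule.
- **That Y1 as a whole is affected.** The pre-AI diagnosis in Y1 is given before that slide's call is shown. Only the post-AI diagnosis carries that cue.

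**Conclusion.** The point holds as a limit on interpretation. Every reader who sees a slide with AI gets the same LEAP call, and kappa is the only planned measure of inter-reader agreement. The plan therefore cannot separate agreement on the truth from agreement on LEAP in Y2 and post-AI Y1. Kappa alone cannot support a claim of better diagnostic consistency in the sense of more agreement on the correct diagnosis.

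The identity between accuracy and the two agreement shares is exact. The kappa sizes are illustrative: they rest on assumed accuracies, prevalence, following rate and error correlation, on following that ignores the reader's own opinion, and on LEAP errors independent of reader errors. Selective following would change them. The issue concerns one secondary outcome and leaves the primary analysis untouched.

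**What to change.** In 6.2.2 and 7.3.2:

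- Report kappa for X, pre-AI Y1, post-AI Y1 and Y2, so that it is clear which Y1 diagnosis is meant.
- Beside each kappa, give the both-correct and both-wrong shares of pairwise reads on shared slides, pooled over the 45 pairs because one pair shares only about 11 slides per condition.
- Show agreement separately for slides where LEAP was right and where it was wrong, as description only.
- State that a change in kappa is interpreted only together with these shares and accuracy.

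Do not add a rule that AI improves consistency only if the both-wrong share does not rise. The last row of the table shows why: a 95%-accurate LEAP lifts accuracy from 85% to 93% and both-correct from 72.3% to 89.5%, yet both-wrong still goes from 2.3% to 3.5%, and such a rule would deny a genuine improvement.

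The cost is SAP wording and a few table columns. Diagnoses and AI predictions are already captured (5.2.3, 8.1.1) and the reference diagnoses exist (3.8). A higher kappa may have to be described less favourably. The LEAP-incorrect stratum will be small: at an assumed 85% accuracy, about 0.15 × 102 = 15 slides. Section 10.2 reports the study complete and 10.3 reports no amendments, so the addition should be labelled post hoc if results have been seen.

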6.2.3 Concordance Between AI Predictions and Clinicians' Diagnoses

Measurement Time Frame: Periprocedural (at the time of slide review)

Description: The proportion of cases in which AI predictions match clinicians' final diagnoses in each study condition. This will be calculated as the percentage agreement between LEAP predictions and clinician diagnoses. Concordance will be evaluated separately for Conditions X, Y1, and Y2.

6.2.4 Decision-Change Rates

Measurement Time Frame: Periprocedural (at the time of slide review)

Description: In Condition Y1 (AI as Double-Check), the proportion of cases in which a clinician's initial diagnosis is revised after viewing the AI prediction. Decision changes will be categorized as:

- Correct-to-incorrect (C→I): Initial correct diagnosis changed to incorrect after viewing the AI prediction
- Incorrect-to-correct (I→C): Initial incorrect diagnosis corrected after viewing the AI prediction

The net decision-change rate will be calculated, along with the proportion of changes that improved accuracy.

6.2.5 Net Benefit After AI Exposure

Measurement Time Frame: Periprocedural (at the time of slide review)

Description: The overall change in diagnostic accuracy attributable to AI assistance, calculated as the difference in accuracy between unaided and aided Conditions:

6.2.6 Clinician Confidence Level

Measurement Time Frame: Periprocedural (at the time of slide review)

Description: Self-reported diagnostic confidence recorded for each case using a 5-point Likert scale:

- 5 = Absolutely Certain
- 4 = Mostly Certain
- 3 = Unsure
- 2 = Very Doubtful
- 1 = Random Guess

Confidence scores will be analyzed to:

- Compare confidence levels across the three conditions
- Assess the relationship between confidence and diagnostic accuracy
- Evaluate whether AI assistance affects clinician confidence (both for correct and incorrect diagnoses)

7. STATISTICAL ANALYSIS PLAN

7.1 General Considerations

7.1.1 Analysis Populations

Intention to Treat (ITT): Participating clinicians will be analyzed according to their originally assigned study arm, regardless of any subsequent switch between arms.

Per-Protocol (PP): Participating clinicians will be analyzed according to the review protocol they actually followed. In cases of arm switching, standard causal inference methods will be applied to adjust for baseline covariates associated with switching behavior.

Primary Analysis Population: The ITT framework will be used for all primary and secondary analyses. Although arm switching is not anticipated, a supplementary PP analysis will be conducted if any switches occur.

7.1.2 Level of Significance

A two-sided alpha level of 0.05 will be used for all comparisons.

7.1.3 Handling of Missing Data

Missing data are not anticipated in this study design, as all diagnostic decisions are captured electronically in real-time.

7.2 Primary Analysis

7.2.1 Primary Endpoint Analysis

Objective: To compare diagnostic performance (accuracy, sensitivity, specificity, PPV, NPV) across the three study conditions.

Diagnostic Performance Metrics:

For each reader and condition, the following metrics will be calculated:

- **Accuracy:** Overall proportion of correct diagnoses
- **Balanced Accuracy:** Average of sensitivity and specificity, accounting for class imbalance
- **Sensitivity:** Proportion of APL cases correctly identified
- **Specificity:** Proportion of non-APL cases correctly identified
- **Positive Predictive Value (PPV):** Proportion of APL predictions that are correct
- **Negative Predictive Value (NPV):** Proportion of non-APL predictions that are correct
- **Weighted F1 Score:** Harmonic mean of precision and recall, weighted by class prevalence

Statistical Method: Friedman test (a non-parametric test for repeated measures across multiple groups) followed by a Wilcoxon signed-rank test.

Rationale: The Friedman test is the appropriate statistical method for this study design because:

- **Within-subject design:** Each reader evaluates cases under all three conditions, creating paired data
- **Non-parametric approach:** Does not assume normal distribution of performance metrics, which is appropriate for bounded proportions (0-1 range)
- **Accounts for reader variability:** Controls for baseline differences among readers by treating each reader as a block, focusing on within-reader differences across conditions
- **Multiple conditions:** Simultaneously tests for differences among three related groups (X, Y1, Y2) rather than requiring multiple pairwise tests
- **Robust to outliers:** Uses rank-based methods that are less sensitive to extreme values

Analysis Procedure:

1. **Global test:** For each performance metric, conduct a Friedman test with the null hypothesis that the distributions of the metric are identical across all conditions.
2. **Significance threshold:** Two-sided alpha = 0.05.
3. **Post-hoc pairwise comparisons:** If the Friedman test yields $p < 0.05$ for a given metric, conduct pairwise Wilcoxon signed-rank tests for all condition pairs.

Wilcoxon Signed-Rank Test Rationale: This paired non-parametric test is appropriate for two-sample comparisons because it preserves the within-reader pairing structure and does not assume normality of the differences between conditions.

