1.3 Study Rationale

Acute promyelocytic leukemia (APL) is a rare but life-threatening subtype of acute myeloid leukemia (AML) that requires urgent diagnosis and treatment initiation. The diagnosis of APL relies on microscopic examination of bone marrow aspirate smears and molecular confirmation. However, inter-observer variability in microscopic evaluation has been reported, and molecular profiling requires additional time and resources. Artificial intelligence (AI) has the potential to augment diagnostic accuracy and efficiency in detecting APL from whole-slide images (WSIs). This study evaluates whether AI assistance through the Leukemia End-to-End Analysis Platform (LEAP) improves clinicians' diagnostic performance compared to unaided review.

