1.5 Study Population

Participants (Readers): Board-certified pathologists and hematologists who routinely perform hematopathology diagnoses. Target enrollment: 10 participants (actual enrollment: 10 participants).

Cases (Pathology Slides): De-identified Wright-Giemsa-stained bone marrow aspirate WSIs with confirmed diagnoses. Each participant reviews 102 slides (34 slides per condition, stratified by APL status).

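### The primary tests in 7.2.1 omit the slide-by-AI variation that readers share through LEAP's single call per slide, so their p-values are too small for claims about new cases, by an amount the documents do not determine.

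*Combined protocol and SAP*

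**What the plan says.** Section 3.4 (Slide Allocation) has every reader work through one common set of slides: "For each participant, the 102 WSIs are randomly divided into three disjoint subsets (SX, SY1, SY2), each containing 34 slides". The split is stratified by APL status, and "Slide allocation is unique to each reader".

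Section 5.1.1 says that before enrollment "the LEAP AI system generates diagnostic predictions for all 102 study cases". Section 3.6 adds that the call shown is binary. There is thus one LEAP answer per slide, the same for every reader who is shown it.

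Section 7.2.1 computes each metric per reader and condition. It then runs a Friedman test over X, Y1 and Y2, followed by pairwise Wilcoxon tests if the Friedman test is significant. One stated reason is that the test "Controls for baseline differences among readers by treating each reader as a block, focusing on within-reader differences across conditions". No slide term, slide resampling or multi-reader multi-case method is planned for the primary endpoint, and no confidence intervals are specified. Section 7.1.2 sets the level: "A two-sided alpha level of 0.05 will be used for all comparisons".

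The question is put in general terms. Section 1.3 asks whether LEAP "improves clinicians' diagnostic performance compared to unaided review", and section 1.7 speaks of detecting APL from bone marrow slides. Nothing limits the conclusion to the 102 slides used.

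**The concern.** Which of the 102 slides LEAP gets right is a single draw of cases. When readers follow LEAP, that draw moves the aided accuracy of all 10 readers in the same direction, so their aided-minus-unaided differences are positively correlated. The tests treat them as 10 independent values.

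This is not the loss of power that comes from ignoring slide difficulty. It works the other way: for a claim about cases in general, the p-value is too small. A set of slides on which LEAP happens to do well could give a significant result even if LEAP brought no average gain over the case population. The trial could then report a general benefit, in a diagnosis that section 1.3 calls life-threatening, on evidence that supports only a statement about this slide set.

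**Working it through.** **Inputs from the documents.** 10 readers (1.5); 102 common slides, split 34/34/34 separately for each reader (3.4); one LEAP call per slide (5.1.1); two-sided alpha 0.05 (7.1.2); Friedman then Wilcoxon on reader-level values (7.2.1).

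**Inputs that are assumptions.** Unaided accuracy and LEAP accuracy, and reliance r, the share of disagreements in which a reader adopts LEAP's call. The documents give none of these, nor APL prevalence.

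**Step 1: is 0.05 held when AI does nothing?** Yes. Exact enumeration of the Friedman test with 10 blocks, 3 conditions, no ties and the chi-square cutoff gives 0.0456. Simulating the design with no AI effect on any slide gives 0.045-0.049.

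**Step 2: the omitted part by hand.** Take readers and LEAP as equally accurate (p), with no other reader or slide variation.
- Variance of one reader's aided-minus-unaided difference: s² = 2p(1-p)/34.
- Two readers' subsets for one aided condition share on average 34 × 34/102 = 11.3 slides. On a shared slide, the covariance of their aided correctness is r²p(1-p).
- Covariance of two readers' differences: (34²/102) × r²p(1-p)/34² = r²p(1-p)/102.
- Correlation: ρ = (r²/102)/(2/34) = r²/6. It does not depend on p.
- True variance of the mean of 10 differences: s²(1 + 9ρ)/10. Expected value of the reader-based estimate: s²(1 - ρ)/10. Ratio: K = (1 + 9ρ)/(1 - ρ).
- Approximate false-positive rate of a reader-only paired t-test: P(|t on 9 df| > 2.262/√K).

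| r | ρ | K | 2.262/√K | rate |
|---|---|---|---|---|
| 0.3 | 0.015 | 1.15 | 2.11 | 0.064 |
| 0.5 | 0.042 | 1.44 | 1.89 | 0.092 |
| 0.6 | 0.060 | 1.64 | 1.77 | 0.111 |
| 1.0 | 0.167 | 3.00 | 1.31 | 0.224 |

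Simulated reader-only t-tests with equal reader and LEAP accuracy agree at r = 0.5 (0.093-0.100). At r = 1.0 they are lower (0.186-0.199), because the simulated readers also differ in their own accuracy, which adds to the variance that is counted.

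**Step 3: the planned Friedman test on accuracy, by simulation.** Reader SD 0.5 and slide SD 1.0 on the logit scale, reader and LEAP accuracy 0.80-0.95, zero average AI effect over the case population, 3,000-4,000 trials per setting (Monte Carlo standard error about 0.003-0.007).

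| r | rejection rate | multiple of 0.05 |
|---|---|---|
| 0.2 | 0.045-0.062 | 0.9-1.2 |
| 0.3 | 0.054-0.061 | 1.1-1.2 |
| 0.4 | 0.067-0.071 | 1.3-1.4 |
| 0.5 | 0.078-0.084 | 1.6-1.7 |
| 0.6 | 0.096-0.102 | 1.9-2.0 |
| 0.75 | 0.117-0.132 | 2.3-2.6 |
| 1.0 | 0.157-0.191 | 3.1-3.8 |

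The Wilcoxon test of X against Y2 behaves similarly (0.15-0.19 at r = 1.0).

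**Step 4: how far the assumptions move this.**
- LEAP errors correlated 0.5-0.8 with slide difficulty: 0.069-0.076 at r = 0.5 and 0.125-0.135 at r = 1.0.
- Slide SD 2.0: 0.103 at r = 0.5 and 0.216 at r = 1.0.
- Sensitivity, assuming 34 APL slides: 0.099 at r = 0.5, 0.163 at 0.7 and 0.213 at 1.0.
- LEAP more accurate than readers, with harm from wrong calls balancing the gain: 0.05-0.11.

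**Step 5: does counting slides repair it?** With slide variance added to reader variance (X against Y2, t on 9 df), the rate is 0.036-0.050 in every setting tried. The reader-only t-test in the same settings gives 0.053-0.199. With a normal reference instead of t, the two-way variance gives 0.066-0.083.

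**The case against.** The best defence is that treating cases as fixed is a legitimate choice of target. The null in 7.2.1 is that a metric has the same distribution in X, Y1 and Y2, and the documents define no case population. For these 102 slides, or if AI alters nothing on any slide, the level is held (step 1). That stands, and it is why limiting the conclusion is an acceptable remedy. It does not dispose of the point, because sections 1.3 and 1.7 word the question generally and no limit is stated.

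A second defence is the separate random split for each reader. A reader might infer from the blocking that the tests count only reader-to-reader variation. The documents do not support that: with a separate split, each reader's difference already carries the sampling noise of ordinary slide difficulty. Only the slide-by-condition part that readers share is missing, and separate splits cannot remove it.

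A third is that low reliance makes the effect negligible. This is correct up to about r = 0.3. But the plan states no reliance, and Y1 and Y2 exist so that LEAP can influence the diagnosis. The inflation is largest where LEAP has most influence.

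**Conclusion.** The point holds for inference beyond the study slides. For each metric, the false-positive rate of the primary tests is about 1.0-1.4 times nominal at reliance up to 40%, about 1.7 times at 50%, about 2 times at 60% and 3-4 times at full reliance. Across all variants tried, the range is about 1 to 4.3 times. These figures rest on assumed accuracies of 0.80-0.95 in the main runs, an assumed reliance and, unless stated otherwise, readers adopting right and wrong LEAP calls equally often.

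It is tempting to say flatly that the error rate is two to three times nominal. The documents do not support that: for accuracy it needs reliance of roughly 0.6-0.9, and no reliance figure is given. Nor are the tests invalid in themselves, since they are sound for these slides. Testing several metrics at 0.05 each is a separate matter and is not included in these figures.

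**What to change.** In 7.2.1, add estimates of Y1-X and Y2-X with a variance that counts both readers and slides, including the shared slide-by-condition part. One workable form is a two-way reader-and-slide variance with a t reference on 9 df, checked by simulation for 10 readers and a 34/34/34 split. Label it post hoc: data collection is complete, and section 10.3 reports no amendments.

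Three versions should be avoided or checked first:
- A percentile two-way bootstrap without calibration is strongly conservative here. Simulated false-positive rates were between 0.003 and 0.03.
- A mixed model with random slide intercepts only does not address the problem.
- A logistic model with a random slide-by-condition effect has only about 1,020/(102 × 3) = 3.3 binary reads per slide-condition cell, so its error rate would need checking before use.

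Otherwise, state in the SAP and the report that the planned tests support conclusions for these 102 slides only.

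The analysis needs no new data, because section 5.2.3 already records each diagnosis by reader, slide and condition. The cost is SAP wording, one re-analysis and a simulation check, with less power and a less favourable p-value. Limiting the conclusion costs one sentence and the general claim.
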